Study Intervention Description	
The following will be offered to all female youth (N=1200):
 
 (1) HIV Testing Services (HTS) via home-based or community based recruitment strategies (2) HIV testing approaches that females can choose from include: (a) oral fluid HIV self-testing (OraQuick ADVANCE® Rapid HIV-1/2 Antibody Test, OraSure Technologies) at their convenience; (b) staff-aided testing at home/mobile site; and (c) a referral to a health care facility where HIV testing will be done by a health care provider (standard facility-based HTS) (3) Behavioral survey at baseline visit (4) SMS HIV test experience satisfaction survey (5) Staff-administered questionnaire about self-testing for females who choose self-testing option. 
For all HIV positive females:
 
All HIV positive females will receive the following;
 
 (1) Point of care (POC) CD4 cell count at baseline (2) Viral load testing using dried blood spot (DBS) at 0 and 12 months (3) Referral for care and treatment; Adaptive linkage to care intervention. All HIV positive participants (N≈108) will be randomized to receive standard referral (N≈54) or standard referral plus SMS message (N≈54) to link to HIV care and treatment services; those who do not link to care within 2 weeks will be re-randomized in a ratio of 1:1 to a second SMS message or a one-time economic incentive to link to care.

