If the participant does not page the number within a 2-week period, the RA will contact them by phone. If they still do not respond, we will trace them using the locator information provided at enrollment. For participants with a positive or indeterminate self-test result, the RA will ascertain a convenient location for conducting the confirmatory test in accordance with current government of Kenya HTS rapid testing algorithm. This may include home based or community, in line with the current recruitment strategy, or at a health care facility. Additionally, a randomly selected proportion (10%) of participants with a negative result will also undergo confirmatory testing for QA/QC purposes per current GoK HIV testing guidelines (NASCOP, 2015). Study staff will be trained and enrolled in the proficiency panel testing QA program with the MoH. When a participant requires confirmatory testing, the RA will follow the standard HTS guidelines for rapid HIV testing, which includes conducting two rapid tests and a tie-breaker if the results are discrepant. At this point if the HIV test is positive, CD4 and VL will be collected and the individual will be invited to enroll in the linkage intervention.

Standard facility based HTS

We will be working with Homa Bay County, Ndhiwa and Mbita health facilities. Participants who choose to test via standard facility based HTS will be given a card with the name of a research assistant/contact person at the facility. Additionally, the participant's detailed locator information will be collected to ensure we can follow up with them as needed. HTS procedures will be conducted per Government of Kenya guidelines. If the participant tests positive, they will be invited to enroll in the linkage intervention.

POC CD4 Testing

At a mobile event, in the home, or facility, if a participant is confirmed positive for HIV, a portable PIMA CD4 analyzer (Alere, Inc., Waltham, Massachusetts, USA) will be used for a Point of Care (POC) CD4 count (Mwau et al., 2013). A finger stick specimen will be taken using an aseptic technique and processed in the PIMA analyzer. Results will be given verbally and in writing to the participant. The results will be used in the counseling for HIV-1 positives. Although WHO new Test and START guidelines recommends immediate treatment irrespective of CD4 count (WHO, 2015), we will collect CD4 at baseline for clinical staging, counseling and treatment preparation purposes.

Viral Load Testing

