In order to determine costs, we will conduct a micro-costing of the cost per HIV-infected person identified under each ‘seek’ and ‘test’ strategy. This will be followed by an incremental cost-effectiveness analysis of the linkage to care interventions among HIV-infected, and a cost analysis of the SMS intervention among HIV-uninfected, women. These costs will include all costs required to deliver each intervention (home visits, staff time, supplies, and monitoring). Data will primarily utilize a micro-costing methodology that uses project expenditure and management records, employing structured costing spreadsheets that record each resource, category (e.g., personnel, supplies), quantity (e.g., hours), and unit costs. The cost data for the self-test group will include costs of obtaining a confirmatory test for those with positive self-testing results. The cost data will be stratified by HIV testing venue (home based, community based (mobile), or referral facility). With these cost data, we will calculate and compare the cost per HIV-infected person identified in each HTC strategy. We will also evaluate the costs of the linkage interventions per individual successfully linked to care. The results of the economic evaluation will allow us to identify the most efficient, affordable way to seek high risk young women and test them. For the linkage interventions, we will utilize the cost data as well as the effectiveness results to compute the ICER for the novel linkage intervention that is used. The ICER will reveal whether the costs of achieving the incremental gains from additional linkage intervention(s) suggest whether it is cost-effective or not. These results will provide novel data on the cost-effectiveness of linkage to care interventions for high-risk females in sub-Saharan Africa.

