Finally, we will conduct a novel economic evaluation, using a societal perspective, to compare the relative utility of the seeking, testing, and linkage to care strategies. This analysis will take into account the economic gains to individuals and households from early diagnosis of HIV and prompt initiation of ART. We will conduct a cost-benefit analysis that focuses on the societal level economic gains that result from individuals who are successfully linked and retained in HIV care and treatment (H. Thirumurthy et al., 2013). We will comprehensively evaluate and model the costs, morbidity averted, new infections averted, and the societal impact of increased household socioeconomic status (SES) resultant from being linked to care and receiving HIV treatment. Data regarding costs will be collected using methods described above. Impacts on SES as a result of higher linkage to care and retention in care will be imputed from other studies we have conducted in Kenya and Uganda showing association between CD4 cell count and employment, income, and domestic (household) labor. We will also explore the possibility of collecting SES data from HIV-infected young women at the time they are enrolled in the linkage to care study and at 12 months. Building on previous work which included a cost effectiveness analysis of HIV prevention interventions (Alsallaq R, Buttolph J, Cleland C, Hallett T, & A., 2013; A. E. [name], [name], I., Agot,

K., Hallett, T., Cleland, C.M., Buttolph, J., Alsallaq, R, 2013) as well as economic evaluations of the effect of HIV treatment on the labor supply in Kenya (Harsha Thirumurthy, Zivin, & Goldstein, 2008), we will expand the work to include the effect of different strategies for HIV seeking, testing, and linkage, which will complete the economic evaluation for the entire HIV continua of care.

Other Analysis

Logistic regression will be used to explore predictors of timely linkage to care among girls newly diagnosed with HIV infection. Potential predictors will include behavioral (e.g, number of sex partners), demographic (e.g., age), and clinical (e.g., baseline CD4) variables assessed at baseline. Interactions between these participant characteristics and treatment conditions of the adaptive intervention also will be explored.

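### The final economic evaluation is called societal, but its costs are provider-side delivery costs; no source is named for participants' travel and time or for facility inputs the project does not pay for

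*Combined protocol and SAP*

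**What the plan says.** Section 13.2 (Cost Effective Analysis) describes two layers of work.

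The first is a micro-costing that feeds the cost per infected young woman found under each seek and test strategy, and the incremental cost-effectiveness ratio for linkage. On scope: "These costs will include all costs required to deliver each intervention (home visits, staff time, supplies, and monitoring"). On source: "Data will primarily utilize a micro-costing methodology that uses project expenditure and management records". On breakdown: "The cost data will be stratified by HIV testing venue (home based, community based (mobile), or referral facility"). No perspective is stated for this layer.

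The second is introduced with the words "we will conduct a novel economic evaluation, using a societal perspective". It compares the seek, test and linkage strategies, and it credits them with gains to individuals and households, illness and infections averted, and improved household socioeconomic status. On its cost inputs it says only: "Data regarding costs will be collected using methods described above".

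Table 1 (Evaluation Plan) gives a single data source for Aim 3, the study's project database.

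On who bears the facility work, the Protocol Summary (Section 6) describes the third test option as "a referral to a health care facility where HIV testing will be done by a health care provider". Section 11.5.1 adds that these participants "will be given a card with the name of a research assistant/contact person at the facility".

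**The concern.** A societal perspective means counting costs whoever bears them, including the participant and the public health system. Here the perspective widens on the benefit side and stays with the provider on the cost side. A cost-benefit result built that way would be reported under a label it does not meet, and net benefit would be overstated by whatever was left out.

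The economic evaluation is one of the two primary objectives, and Section 13.2 says its results will identify the most efficient and affordable way to find and test young women at high risk. If cost capture differs between test options, the societal comparison of those options is not like for like.

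**Working it through.** The documents give no unit cost, delivery cost or cost-effectiveness ratio, so there is no plan figure to reproduce. The check compares the text on each side of the analysis.

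1. **Benefit side (Section 13.2).** Gains are societal: individual and household economic gains, morbidity and infections averted, household socioeconomic status. They are to be imputed from other studies. Collecting socioeconomic data from HIV-infected participants is raised only as a possibility, and such data would not measure what a test cost the participant.

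2. **Cost side (Section 13.2).** The societal step refers back to the micro-costing and adds no cost source of its own. The items given as examples there (home visits, staff time, supplies, monitoring) are all provider items.

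3. **Is there a participant-cost instrument anywhere?** The baseline survey topics (Section 11.5.1), the SMS survey topics (Section 11.6.2, an expressly open list), the exit interviews (Section 11.6.3), the schedule (Appendix A) and Table 1 name no item on travel cost, waiting time or lost earnings. The protocol does recognise the burden: Section 17.5.1 notes that transport can be a barrier to reaching facilities.

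4. **Are facility inputs covered?** They are in scope, because all delivery costs are to be counted and the referral facility is a named stratum. What is missing is a source. Facility testing is done by a health care provider, whose time and supplies need not appear in project records. The plan expressly adds the cost of confirmatory testing to the self-test group, but makes no matching provision for valuing the facility's own resources. The treatment whose gains are counted raises the same question: Section 17.5.1 says HIV laboratory tests and medicines are free to patients at the facilities, and no source is named for their cost.

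5. **Direction.** Staff-aided testing at home or at the mobile event is done by study staff, so its cost reaches project records. Facility testing adds a trip by the participant and work by non-study staff. If project records alone fill the facility stratum, the shortfall is probably largest there. This is an inference; the plan does not say it.

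6. **Size.** If a cost *c* per person tested is left out, the cost per case found is too low by *c* / *y*, where *y* is the yield. Section 15.11 expects *y* of about 9% (55/636 = 8.6%) and uses 14% as its detectable alternative; 5% is assumed here as a low value. For each KSh 100 left out (an assumed round sum):
   - *y* = 5%: 100 / 0.05 = KSh 2,000
   - *y* = 9%: 100 / 0.09 = KSh 1,111
   - *y* = 14%: 100 / 0.14 = KSh 714

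   This shows only that small per-test omissions are multiplied about 7 to 20 times per case found. The documents give no value for *c* under any test option.

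**The case against.** The plan has a fair defence, and much of it stands.

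- **Ministry facility costs.** A reader might infer that the plan leaves these out. It does not say so: all delivery costs count, the referral facility is a stratum, and project records are the main source rather than the only one. A contact person at the facility, possibly a research assistant, also means some facility-side cost may be project cost. What survives is the unnamed source.
- **The cost-per-case endpoints.** A reader might infer that these primary-objective outcomes are biased because bus fares are missing. They carry no societal label, and a delivery costing that excludes participant costs is a legitimate provider analysis. The perspective mismatch belongs to the final step; only the question of how facility inputs are valued touches both.
- **One option only.** A reader might infer that participant costs are missing for facility testing alone. They arise elsewhere too: participants attend mobile events, a minor who arrives without a parent must return with one (Section 11.2), and self-testers with a positive or indeterminate result may have the confirmatory test at a facility (Section 11.5.1).
- **A monetary size.** A reader might divide the KSh 400 linkage payment (Section 11.6.1) by the 9% yield. That payment is an incentive to reach HIV care, not a measured testing trip; Section 10.2 starts sampling within walking distance of the facility catchment; and 9% is an overall yield, not one for facility testers. The result would not estimate anything in this study.

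The defence does not reach the central point: the final step is called societal, its costs come from the delivery costing, and participant costs are collected nowhere.

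**Conclusion.** The mismatch is real and should be corrected. As written, the final economic evaluation sets societal benefits against provider-side costs and is not a societal analysis. Two inputs have no source: participants' travel and time, and facility resources the project does not pay for.

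The omitted costs probably weigh most on facility-based testing, so the likely lean is in that option's favour. This assumes that the facility stratum is filled largely from project records and that facility testers travel more than others. A reader might go further and conclude that the ranking of test strategies is wrong; the documents do not support that, because they give neither the omitted costs nor the delivery costs they would be compared with.

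The cost-per-case endpoints can stand as a provider-perspective analysis, provided they are labelled that way and facility tests are costed from more than project records.

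**What to change.** State the perspective of each economic analysis in Section 13.2 and Table 1, and choose one of two routes.

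- **Relabel.** Describe the cost side of both the micro-costing and the final evaluation as a programme (provider) perspective. This costs nothing.
- **Keep the societal label.** Add two items, travel cost and time away, to the 2-week SMS survey, which goes to every participant. Allow a not-yet-tested answer. Self-testers who page are sent this survey at once, so ask the same items at any later confirmatory test. The 12-month exit interview is the wrong place: it reaches only the HIV-positive cohort and about 185 high-risk negatives, and would rely on year-old recall. These items cover testing; a societal comparison of linkage strategies needs the same questions about the trip to care.

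On either route, value facility tests with Ministry or facility unit costs, name that source in Table 1, and apply the same cost categories to all three test options. If gains from treatment stay in the model, name a source for its cost too. A sensitivity analysis over the facility unit cost, and over participant costs if collected, would show whether the ranking depends on them.

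The burden is at most two short SMS questions, their repeat at the later contacts noted above, and a unit-cost lookup.

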14. LABORATORY SPECIMENS AND BIOHAZARD CONTAINMENT

14.1 Local Laboratory Specimens

HIV infection

- HIV testing
- CD4 cell count
- Viral load (VL) testing

Local laboratory Kenya Medical research, CDC laboratory will perform testing for viral load and quality assurance for CD4 and rapid HIV tests. The CDC research lab in Kisumu has an elaborate internal and External Quality Assurance (EQA) programs.

The study will adhere to standards of good laboratory practice, SSP manual, and local SOPs for proper collection, processing, labeling, transport, and storage of specimens. Specimen collection, testing, and storage at the local Lab will be documented using the **Data Management System (LDMS)** as described in the SSP Manual.

Quality Control and Quality Assurance Procedures

The CDC lab staff will follow up directly with site staff to resolve any QC or quality assurance (QA) problems identified through proficiency testing and/or on-site assessments. Throughout the course of the study, the lab will select a random sample of specimens to test for QA purposes.

QC for HIV diagnostic testing

Algorithms for HIV diagnostic testing are provided in the protocol and the SSP Manual. Participants will be tested for HIV infection status following current GoK guidelines. Participants with a positive or indeterminate result using the oral self-test kit will undergo confirmatory testing by study staff using a rapid blood test. In addition, a proportion of participants with a negative result from the oral self-test will also undergo confirmatory testing per current GoK guidelines for QA/QC purposes. HIV testing using blood samples will be subjected to quality assurance procedures. Proficiency panel testing from a proportion of tested samples will be done for both positive and negative per current GoK testing guidelines. We will follow these guidelines and will train our HTS staff on proficiency testing, i.e., staff conducting the tests will be subjected to testing of blinded panels of blood samples two or three times a year as part of quality assurance.

QC for HIV RNA monitoring

Quantitative HIV RNA (viral load) testing will be performed at Kisumu CDC lab at baseline and at 12 month follow up in any subject with confirmed HIV infection. QA for the VL testing will be done at the CDC lab and will fall under their QA system that has been established.

QC for CD4 cell count determination

For participants who test positive, CD4 cell count testing will be performed at the time when HIV infection is confirmed using PIMA POC machines which have been validated in Kenya and used

for the recent national household KAIS survey. QA will be carried out by CDC lab, every third sample will be sent to the CDC lab for re-testing.

Specimen Preparation, Handling and Shipping

No specimens will be stored long-term. Specimens will be prepared according to the protocol and the WHO guidelines on biosafety. All containers will be clean. All containers will be appropriately labeled. Specimens that need to be transported to the CDC lab will be packaged in the triple packaging system. Specimens will be placed in the primary receptacle, then placed in leak-proof secondary containers, (boxes fitted with racks), and a third layer of outer packaging to protect the secondary container from damage. The box will be regularly decontaminated.

Biohazard Containment

As the transmission of HIV and other blood-borne pathogens can occur through contact with contaminated needles, blood, and blood products, appropriate blood and secretion precautions will be employed by all personnel in the drawing of blood and shipping and handling of all specimens for this study, as currently recommended by the U.S. CDC. All infectious specimens will be transported in leak proof containers.

Sample storage

Study site staff will store all DBS samples collected in this study, at -20°C or -80°C, until all protocol-related testing has been completed, including QC testing and other testing performed at the site.

15. SAFETY MONITORING STRUCTURE

15.1 Safety Monitoring

In order to ensure participant safety, a multi-tiered communication network will be established between the study staff, field study coordinator, field site director, project manager, biostatistician, principal investigators, and NIAID project officer and medical officer to monitor participant safety and who will compose the Protocol Safety Review Team (PSRT). The PSRT will be chaired by the PIs. Regular (monthly and if needed more frequent) Skype calls will occur between the principal investigators, field site director, biostatistician, project manager and the field study coordinator and any issues will be communicated to the larger scientific team and brought immediately to the attention of the project officer and medical officer. Any serious adverse events (AEs) will be reported to the IRBs following protocols outlined below. The reports of safety issues will be reviewed by the study scientific team (PIs, biostatistician). Any SAE will be reported to NIAID, MoH, and IRBs as outlined in the next pages. The data manager will compile routine safety reports with the field study coordinator for review by the PSRT. The content, format, and frequency of the safety data reports will be agreed upon by the PSRT in advance of study implementation.

15.2 Level of Severity for Adverse Events (AE)

As with any evaluation involving medical interventions, potential adverse events (AEs) are expected. However, we expect that the risk of an adverse event as a result of study-related activities is minimal, our study does not involve a pharmacological agent. Possible adverse events in this population may include risk of distress and embarrassment during collection of personal data such as sexual risk behaviors. Taking a finger stick blood sample for HIV testing may cause a little pain, but poses minimal risk of infection because we will use sterile equipment and follow infection control and prevention procedures. All AEs reported by or observed in enrolled study participants will be documented regardless of severity and presumed relationship to study procedures.

Adverse events

An AE is any untoward medical occurrence in a participant for which there is a reasonable possibility that the experience may have been caused by the procedure; All AEs will be graded according to their intensity using the most recent DAIDS AE Grading Table available at: <http://rsc.tech-res.com/safetyandpharmacovigilance>. Serious Adverse Events (SAEs) (described below) will be recorded and reported to the Provincial Director of Health and the regulatory bodies using both DAIDS AE grading table and the implementing partner's AE severity scale (listed below).

Serious Adverse Events (SAE):

- Results in death,
- Is life-threatening,
- Requires inpatient hospitalization or prolongation of existing hospitalization,
- Results in persistent or significant disability/incapacity,

- Is a congenital anomaly/birth defect, or
- Is an important medical event that may not be immediately life-threatening or result in death or hospitalization but may jeopardize the patient or may require intervention to prevent one of the other outcomes listed in the definition above.

Adverse Events/Serious Adverse Events Severity Scale

- **Grade 1 (Mild):** events require minimal or no treatment and do not interfere with the patient's daily activities.
- **Grade 2 (Moderate):** events result in a low level of inconvenience or concern with the therapeutic measures. Moderate events may cause some interference with functioning.
- **Grade 3 (Serious):** events interrupt a patient's usual daily activity and may require systemic drug therapy or other treatment. Serious events are usually incapacitating.
- **Grade 4 (Life threatening):** any adverse drug experience that places the patient or participant, in the view of the investigator, at immediate risk of death from the reaction as it occurred, i.e., it does not include a reaction that had it occurred in a more severe form, might have caused death.
- **Grade 5 (Death)**

